8.1.3.1 Primary Efficacy Analysis

The primary efficacy variable will be the change from baseline to Week 52 on the PSPRS total score. The primary efficacy analysis will utilize a likelihood-based, mixed-effects model, repeated measures (MMRM) analysis of the change from baseline for each post-baseline and compare each ABBV-8E12 dose group with the placebo group. The model, which uses all observed data, will include fixed, categorical effects for treatment, site, visit, baseline score-by-visit interaction and treatment-by-visit interaction, with continuous fixed covariates for the corresponding baseline score. The primary comparison will be the contrast between each ABBV-8E12 dose group and placebo at Week 52. The treatment group differences at earlier visits will be assessed as secondary. An unstructured (co)variance structure will be used to model the within-subject errors. Satterthwaite's approximation will be used to estimate denominator degrees of freedom and the Type III sum-of-squares for the Least Square (LS) means will be used to estimate treatment group differences.

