4.3 Sample Size

Approximately 330 PSP subjects (110 subjects/group) will be enrolled and randomized into two ABBV-8E12 dose groups and the placebo group with 1:1:1 randomization ratio. This sample size has ~90% power to detect an ABBV-8E12 effect size (vs. placebo) of 0.56 for the high dose and 0.28 effect size for the low dose on the PSPRS total score changes from baseline at Week 52 using the Bonferroni method to control for multiplicity due to multiple comparisons between two doses and placebo at the two-sided 5% significant level. A no data rate of 25% at Week 52 is assumed in this sample size calculation using East version 6.3.1 (Cytel).

In Japan, a total of 24 subjects (8 subjects/arm) randomized will have 80% probability to detect the consistent treatment effect among three regions (Japan, North America including US/Canada, and European countries including Australia assuming 7%, 54%, and 39% of the total 330 PSP subjects are randomized in three regions, respectively). This calculation is based on Method 2¹ and assumes that the significance level for comparison of each ABBV-8E12 dose vs. placebo is two-sided 2.5% and the dropout rate is 25% in all regions.

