Randomization and study drug administration are the last activities of the Day 1 Visit after the site completes other study procedures and verifies that the subject is eligible to participate in the study. From the definition of "baseline," it is clear that a baseline for a specific measurement is the last non-missing observation taken up to and on the Day 1 Visit (the Randomization Visit). At the computation level, the value of "baseline" for an efficacy or safety assessment is determined using the Rx Day associated with the visit. Namely, baseline value is determined by taking the last non-missing observation obtained before the time of first dosing on Rx Day 1. If an SAE occurs on the first dosing day, the event will be reported as a post baseline event and the related safety assessments will be considered post-baseline data as well.

Definition of Analysis Windows

To perform longitudinal data analysis, observations that are obtained after the first day of study drug administration will be assigned to an analysis "week" associated with the Rx Days that are corresponding to the observations. Unless otherwise specified, efficacy observations and safety observations no more than 45 days after the last dose of study drug will be included in analyses for the double-blinded period. Safety observations later than 45 days, but no more than 20 weeks, after the last dose of study drug will be included for the post-treatment follow-up period safety analysis. The intervals presented below for

each schedule visit (Rx Days X through Y) include both Rx Days X and Y. The nominal day for each scheduled visit is defined in "Activities" row in [Table 2](#).

For measurements that are planned to be collected during double-blind treatment period at Weeks 12, 24, 36, and 52, i.e., PSPRS, SEADL, PGI-C, PSP-QoL and UPDRS Part II, observations will be mapped to an analysis "week" according to the following windows defined by Rx day.

- Week 12 Rx Days 2 through 126
- Week 24 Rx Days 127 through 210
- Week 36 Rx Days 211 through 308
- Week 52 Rx Days > 308

For measurements that are planned to be collected during double-blind treatment period at Weeks 8, 20, 32, and 48, i.e., RBANS, Color Trails Test (Parts 1 & 2), letter fluency, EQ-5D, and NNIPPS-PPS, observations will be mapped to an analysis "week" according to the following windows defined by Rx day.

- Week 8 Rx Days 2 through 98
- Week 20 Rx Days 99 through 182
- Week 32 Rx Days 183 through 280
- Week 48 Rx Days > 280

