10.2 Primary Analysis of Primary Efficacy Endpoint

The primary efficacy endpoint is the change from baseline to Week 52 visit on the PSPRS total score. The primary analysis population will be subjects in the ITT dataset and the primary analysis will be a likelihood-based, mixed-effects model, repeated measures (MMRM) analysis of the change from baseline to each post-baseline assessment up to and including Week 52. The model will include fixed, categorical effects for treatment, site, visit, baseline score-by-visit and treatment-by-visit interactions, with continuous fixed

covariates for baseline score. The primary comparison will be the contrast between each ABBV-8E12 dose group and placebo group at Week 52. Contrasts between each ABBV-8E12 dose group and placebo at Weeks 12, 24, and 36 and overall across the treatment period will be obtained and will be considered as secondary. An unstructured (co)variance structure will be used to model the within-patient errors. If this analysis fails to converge, compound symmetry (co)variance structures will be tested. The same (co)variance structure will also be used for all MMRM analyses for secondary efficacy variables. Satterthwaite's approximation will be used to estimate denominator degrees of freedom.

The following statistics will be presented on the statistical table of MMRM analysis for change from baseline to each visit (Weeks 12, 24, 36, and 52): descriptive statistics (number of non-missing observations, mean, standard deviation, minimum and maximum) for each treatment group. LS mean and standard error within group will be presented for each treatment group. LS mean, standard error, 95% confidence interval and two-sided nominal *P* value of treatment difference comparing each ABBV-8E12 dose group with placebo will also be presented for each post-baseline visit. The LS mean, standard error, 95% confidence interval and two-sided nominal *P* value of treatment difference comparing each ABBV-8E12 dose group with placebo across the treatment period will be included in the output as well.

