10.3 Secondary Efficacy Analyses

10.3.1 Analysis of Secondary Efficacy Variables

The secondary efficacy variables include change from baseline in the following score:

- Unified Parkinson's Disease Rating Scale (UPDRS) Part II score
- Clinical Global Impression of Change (CGI-C) score (the score itself indicate change)
- Midbrain atrophy measured by volumetric MRI change from baseline
- Schwab and England Activities of Daily Living Scale (SEADL) score
- Clinical Global Impression of Severity (CGI-S) score
- PSP Quality of Life (PSP-QoL) total, subscales and VAS scores
- PSPRS domain scores
- Regional atrophy measured by volumetric MRI – third ventricle, frontal lobes, superior cerebellar peduncle, brainstem, whole brain
- PSP Staging System (PSP-SS) (composite of dysphagia and gait items from PSPRS) score
- Time to loss of ability to walk independently as measured by PSPRS item 26, which is the Rx day of the first time when the post-baseline item 26 score is 3 or 4.

UPDRS Part II score, CGI-C score, SEADL score and the midbrain atrophy measured by volumetric MRI are key secondary efficacy variables, and the Week 52 contrasts for these variables for ABBV-8E12 doses vs placebo will be included in the multiplicity adjustment for the overall FWER control. Volumetric MRI atrophy variables (third ventricle, frontal lobes, superior cerebellar peduncle, brainstem, whole brain), PSP-QoL total score and subscale and VAS scores, PSPRS domain scores, CGI-S score, PSP-SS score and time to loss of ability to walk analysis (measured by PSPRS item 26) will not be included in the multiplicity adjustment for the overall FWER control. The MMRM method used for the primary efficacy analysis will be applied to analyze the change from the baseline to each post-baseline assessment up to and including Week 52 for all secondary variables except time to loss of ability to walk independently as measured by PSPRS item 26. The model will include fixed, categorical effects for treatment, site, visit, baseline score-by-visit and treatment-by-visit interaction, with continuous fixed covariate for baseline score and the baseline score-by-visit interaction in the model. The comparison will be the contrast between each ABBV-8E12 dose group and placebo group at each post-baseline visit. For

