10.6 Handling of Multiplicity

Pairwise comparisons between each ABBV-8E12 dose group and the placebo group will be performed with two-sided tests. Hochberg procedure² will be used for the efficacy analysis to handle multiplicity of comparisons between multiple ABBV-8E12 doses and placebo at the pre-specified significance level at the interim analysis ($\alpha = 0.00001$ at each futility interim analysis), which is described in the DMC Charter.

[figure not shown]
For the final analysis, a graphic approach³ will be used to control overall family wise error rate due to multiple comparisons for primary and key secondary efficacy endpoints for multiple ABBV-8E12 doses. The overall α for the final analysis is 0.04998 after accounting for α spending at interim futility analyses. This α will be split equally between two dose groups to test the efficacy endpoints in the primary and key secondary families within each dose level at Week 52. The order of efficacy endpoints to be tested is PSPRS

total score change at Week 52, UPDRS-II score change at Week 52, CGI-C score at Week 52, midbrain atrophy measured by volumetric MRI change from baseline at Week 52, SEADL score change at Week 52 (Table 3). The primary endpoint will be tested first followed by the secondary endpoints and α could be propagated between two doses and two families of hypotheses testing based on the graphic approach (Figure 2). In the graph, the arrows specify the α transfer paths. Once an endpoint is rejected (i.e., deemed significant) at its assigned significance level, its significance level will be transferred to subsequent endpoint(s) following the arrow(s). If more than one arrow originates from an endpoint, the significance level for this endpoint (once rejected) will be split between multiple subsequent endpoints following the arrows. The numbers on the arrows denote the weights for transferring and (possibly) splitting significance levels. Specifically, the weight 1 denotes 100% transfer of significance level. The number underneath of each hypothesis is the original weight for α splitting assigned to the hypothesis. The overall type I error rate for this trial will be controlled at the two-sided 5% level. Nominal P values and multiplicity adjusted P values for all variables listed in Table 3 will be presented in a table.

Table 3. Hypotheses Testing Order in The Graphical Testing Approach

Efficacy Endpoints Family	Ordered Efficacy Endpoints	Hypotheses	

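### The SAP's covariance fallback for the primary MMRM does not require visit-specific variances, so the Week 52 test could exceed its level if the fallback is used

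*SAP*

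**What the plan says.** Protocol Section 8.1.3.1 specifies one structure and no alternative: "An unstructured (co)variance structure will be used to model the within-subject errors". SAP Section 10.2 repeats this ("An unstructured (co)variance structure will be used to model the within-patient errors") and adds the only fallback in either document: "If this analysis fails to converge, compound symmetry (co)variance structures will be tested". The next SAP sentence extends the choice: "The same (co)variance structure will also be used for all MMRM analyses for secondary efficacy variables". SAP Section 10.3.1 then says of the secondary variables: "The MMRM method used for the primary efficacy analysis will be applied to analyze the change from the baseline". Both documents specify Satterthwaite degrees of freedom. Neither specifies a robust standard error for the MMRM.

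The contrast that carries the alpha is each dose against placebo at Week 52. SAP Section 10.6 sets the final alpha at 0.04998, which "will be split equally between two dose groups to test the efficacy endpoints".

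**The concern.** The fallback sentence names one family. It does not say whether the variances must be equal across visits, in what order forms are tried, or how one is chosen once several have been tested.

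The standard error is model-based, so it inherits the assumed covariance. Equal-variance compound symmetry replaces the Week 52 variance with roughly the average over Weeks 12, 24, 36 and 52. In a progressive disease the spread of change scores may well widen with time. The average would then understate the Week 52 variance, and the primary test would reject too often.

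The carry-over sentence adds a second gap. Read literally, the PSPRS fit fixes the structure for every secondary MMRM. A secondary that fails to converge when PSPRS has converged then has no stated fallback. If PSPRS does fall back, the key secondaries follow it even where their own unstructured fits would converge.

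**Working it through.** **Inputs from the documents.** 110 subjects per arm and ~90% power at effect size 0.56 for the high dose (SAP 4.3). "A no data rate of 25% at Week 52 is assumed in this sample size calculation" (SAP 4.3). Alpha per dose 0.04998/2 = 0.02499, two-sided, z = 2.2416 (SAP 10.6). Four post-baseline PSPRS visits: "Weeks 12, 24, 36, and 52, i.e., PSPRS, SEADL, PGI-C, PSP-QoL and UPDRS Part II" (SAP 6.2).

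**Inputs that are assumptions.** SDs by visit, within-subject correlations, number of pseudo-sites, and dropout completely at random.

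**The plan's own figure.** With 110 × 0.75 = 82.5 evaluable per arm, power = Φ(0.56 × √(82.5/2) − 2.241) = Φ(1.355) = 0.912, in line with the stated ~90% for the high dose. This confirms sample size, alpha and dropout. It does not depend on the fallback.

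**Closed form, complete data.** Under equal-variance compound symmetry, the ratio of model SE to true SE at Week 52 is r = √(mean of the four squared SDs)/SD at Week 52. Type I error is 2 × (1 − Φ(2.2416 × r)). With a visit-specific variance, the interval is wider by the factor 1/r.

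| Assumed SDs, Weeks 12/24/36/52 | r | Type I error | Interval width change |
|---|---|---|---|
| 1 / 1 / 1 / 1 | 1.000 | 2.50% | none |
| 0.90 / 0.93 / 0.96 / 1 | 0.948 | 3.35% | +5.5% |
| 0.75 / 0.825 / 0.90 / 1 | 0.874 | 5.02% | +14.5% |
| 0.50 / 0.65 / 0.80 / 1 | 0.760 | 8.83% | +31.5% |
| 1.25 / 1.175 / 1.10 / 1 | 1.135 | 1.10% | narrower |

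For the fourth row: (0.25 + 0.4225 + 0.64 + 1)/4 = 0.578, whose square root is 0.760; 2.2416 × 0.760 = 1.704, giving 8.8%.

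**Simulation with dropout.** REML fits with 110 per arm, 30 pseudo-sites as fixed effects, treatment-by-visit means, no baseline term, 25% monotone dropout by Week 52 and Satterthwaite degrees of freedom; 3,000 datasets (6,000 dose tests) per case. Monte Carlo SE is about 0.3 points near 2.5% and 0.4–0.6 points at the inflated rates.

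| Correlation; Week 12/Week 52 SD ratio | Equal-variance CS | Het. CS | Het. AR(1) | Het. Toeplitz |
|---|---|---|---|---|
| AR 0.8; 1.0 | 3.18% | 2.65% | 2.70% | 2.70% |
| AR 0.8; 0.75 | 6.75% | 2.60% | 2.75% | 2.78% |
| AR 0.8; 0.50 | 11.42% | 2.63% | 2.72% | 2.73% |
| Exchangeable 0.6; 1.0 | 2.67% | 2.67% | 2.52% | 2.70% |
| Exchangeable 0.6; 0.75 | 5.57% | 2.63% | 2.52% | 2.67% |
| Exchangeable 0.6; 0.50 | 10.35% | 2.60% | 2.50% | 2.65% |

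**Second, independent simulation.** This one included baseline-by-visit terms, 20 pseudo-sites and a fixed 240 degrees of freedom, with 1,500 trials per case. Equal-variance compound symmetry gave 5.2% for SDs 8/9/10/11, 8.7–9.9% for 6/8/10/12, 13.4% for 4/7/10/13, and 2.3% for flat SDs. Heterogeneous compound symmetry gave 1.8–2.4% and unstructured 2.1–2.4%. For flat SDs with autoregressive correlation the two simulations differ slightly (3.2% against 2.3%), so I draw nothing from that case. They agree that unequal variances drive the inflation.

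**How likely is the trigger?** The PSPRS matrix has 4 × 5/2 = 10 parameters for about 330 subjects. In 1000 simulated unstructured fits (normal data, no site effects, not SAS) none failed, an upper 95% bound of about 3/1000 = 0.3%. At the worst simulated rate, the unconditional increase is at most about 0.003 × (11.4 − 2.5) = 0.03 percentage points. CGI-C has eight post-baseline visits (SAP 6.2), hence 8 × 9/2 = 36 parameters. Its convergence was not examined.

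**The case against.** Harm needs three things together: the unstructured fit fails, the analyst takes the equal-variance form, and the SD rises. The first is improbable for PSPRS. On the second, the SAP's plural wording may already include heterogeneous compound symmetry, which held the level in every case. On the third, the documents give no SD by visit, and a falling SD makes the test conservative. All of this stands, and it keeps the priority low. It does not supply the missing rule: the wording permits a visit-specific form but does not require one.

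The carry-over sentence can also be read as plain: the PSPRS structure governs. On that reading, choosing per endpoint changes the SAP's rule and does not merely clarify it. That is fair. But the literal rule is what leaves a non-converging secondary, such as eight-visit CGI-C, without a fallback.

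The error rates were computed for PSPRS only, and neither the convergence check nor the main simulation fits the full SAP model. That also stands, so the figures are indicative. Finally, stating that the compound symmetry fallback uses visit-specific variances would be a shorter edit and would remove the type I error problem. It would not settle the secondary endpoints.

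**Conclusion.** The point holds as a conditional, low-priority gap in pre-specification. If equal-variance compound symmetry is used and the SD of PSPRS change rises toward Week 52, the per-dose test at a nominal 2.5% runs at about 3.4% to 8.8% with complete data over the assumed SD ratios 0.90 to 0.50. With 25% dropout it runs at about 5.6% to 11.4% over ratios 0.75 to 0.50. With equal SDs and complete data there is no inflation. The unconditional effect on the primary analysis is very small because the fallback is unlikely to be needed. The primary result is not at material risk, but the written rule can give a wrong error rate when followed, and it can be corrected cheaply.

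**What to change.** In SAP Section 10.2, replace the fallback sentence with:

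> If the unstructured model does not converge for an endpoint, structures with visit-specific variances will be fitted to that endpoint in this order and the first that converges will be used: heterogeneous Toeplitz, heterogeneous AR(1), heterogeneous compound symmetry.

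Replace the carry-over sentence with:

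> The same rule will be applied separately to each secondary efficacy variable analyzed by MMRM.

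Keep Satterthwaite's approximation. Another order of the three would do equally well if fixed in advance. A closing clause on what happens if none converges would complete the rule.

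The cost is two sentences, with no departure from the protocol's unstructured primary model or its degrees-of-freedom method. If the fallback is reached and variance does rise, intervals are wider than under equal-variance compound symmetry by the amounts in the first table; that widening is the correction itself.

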10.3 Secondary Efficacy Analyses

10.3.1 Analysis of Secondary Efficacy Variables

The secondary efficacy variables include change from baseline in the following score:

- Unified Parkinson's Disease Rating Scale (UPDRS) Part II score
- Clinical Global Impression of Change (CGI-C) score (the score itself indicate change)
- Midbrain atrophy measured by volumetric MRI change from baseline
- Schwab and England Activities of Daily Living Scale (SEADL) score
- Clinical Global Impression of Severity (CGI-S) score
- PSP Quality of Life (PSP-QoL) total, subscales and VAS scores
- PSPRS domain scores
- Regional atrophy measured by volumetric MRI – third ventricle, frontal lobes, superior cerebellar peduncle, brainstem, whole brain
- PSP Staging System (PSP-SS) (composite of dysphagia and gait items from PSPRS) score
- Time to loss of ability to walk independently as measured by PSPRS item 26, which is the Rx day of the first time when the post-baseline item 26 score is 3 or 4.

UPDRS Part II score, CGI-C score, SEADL score and the midbrain atrophy measured by volumetric MRI are key secondary efficacy variables, and the Week 52 contrasts for these variables for ABBV-8E12 doses vs placebo will be included in the multiplicity adjustment for the overall FWER control. Volumetric MRI atrophy variables (third ventricle, frontal lobes, superior cerebellar peduncle, brainstem, whole brain), PSP-QoL total score and subscale and VAS scores, PSPRS domain scores, CGI-S score, PSP-SS score and time to loss of ability to walk analysis (measured by PSPRS item 26) will not be included in the multiplicity adjustment for the overall FWER control. The MMRM method used for the primary efficacy analysis will be applied to analyze the change from the baseline to each post-baseline assessment up to and including Week 52 for all secondary variables except time to loss of ability to walk independently as measured by PSPRS item 26. The model will include fixed, categorical effects for treatment, site, visit, baseline score-by-visit and treatment-by-visit interaction, with continuous fixed covariate for baseline score and the baseline score-by-visit interaction in the model. The comparison will be the contrast between each ABBV-8E12 dose group and placebo group at each post-baseline visit. For

CGI-C analysis, the dependent variable is the CGI-C score itself, baseline CGI-S score will be used in the MMRM model as a covariate and no baseline score-by-visit interaction in the model. For the volumetric MRI variables, the model will have a second covariate, a measure of head size (i.e., estimated pseudo total intracranial volume).

The following statistics will be presented on the statistical table of MMRM analysis for change from baseline to each post-baseline visit: descriptive statistics (number of non-missing observations, mean, standard deviation, minimum, and maximum) for each treatment group. LS mean and standard error within group will be presented for each treatment group. LS mean, standard error, 95% confidence interval and two-sided *P* values of treatment difference comparing each ABBV-8E12 dose group with placebo will also be presented for each post-baseline visit. The overall LS mean, standard error, 95% confidence interval and two-sided raw *P* values of treatment difference comparing each ABBV-8E12 dose group with placebo across the treatment period will be included in the output as well.

Responder analysis will be conducted for CGI-C variable. The responses of "Very much improved," "Much improved," "Minimally improved" and "No change" on the CGI-C will be defined as responders. Repeated measure analysis of responders over time on CGI-C responder status will be conducted using a generalized estimation equation (GEE) model with a logit link function to compare the probability of being a responder between each ABBV-8E12 dose and placebo. The model will include fixed, categorical effects for treatment, site, visit and treatment-by-visit interaction in the model using exchangeable working correlation structure. The odds ratio and corresponding 95% confidence interval will be provided for each ABBV-8E12 dose vs placebo at each visit. This responder analysis will not be included in multiplicity adjustment for FWER.

The time to loss of ability to walk independently as measured by PSPRS item 26 will be analyzed using log-rank test to compare median time to loss of ability to walk between placebo and ABBV-8E12 arms.

If both doses are statistically significant on the primary endpoint (PSPRS total score change from baseline at Week 52) after multiplicity adjustment, the contrast between pooled two ABBV-8E12 doses vs. placebo will also be obtained from the MMRM or GEE models for the primary and all secondary efficacy variables.

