Responder analysis will be conducted for PGI-C variable. The responses of "Very much improved," "Much improved," "Minimally improved" and "No change" on the PGI-C will be defined as responders. Repeated measure analysis of responders over time on PGI-C responder status will be conducted using a GEE model with a logit link function to compare probability of being a responder between each ABBV-8E12 dose and placebo. The model will include fixed, categorical effects for treatment, site, visit and treatment-by-visit interaction using an exchangeable working correlation structure in the model. The odds ratio and corresponding 95% confidence interval will be provided for each dose group at each visit. This responder analysis will not be included in multiplicity adjustment for FWER.

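### The CGI-C responder GEE leaves out baseline CGI-S and is fitted unweighted to observed visits, so it gives up some power and, unlike the CGI-C MMRM, can be biased when dropout depends on earlier scores

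*SAP*

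**What the plan says.** SAP 10.3.1 analyses CGI-C in two ways. The score itself goes into the MMRM, where "baseline CGI-S score will be used in the MMRM model as a covariate and no baseline score-by-visit interaction in the model". The score is also dichotomised, with no change or any improvement counted as response, and analysed by a logit GEE: "The model will include fixed, categorical effects for treatment, site, visit and treatment-by-visit interaction in the model using exchangeable working correlation structure". The output is an odds ratio for each dose against placebo at every visit. On error control the SAP states: "This responder analysis will not be included in multiplicity adjustment for FWER".

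CGI-S is scheduled at screening and on Day 1 (Protocol Table 7), so the covariate is already collected. CGI-C has eight post-baseline visits (SAP 6.2).

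On missing data, SAP 4.3 says: "A no data rate of 25% at Week 52 is assumed in this sample size calculation". That calculation is for PSPRS. The multiple-imputation and tipping-point analyses in SAP 10.5.1 concern the PSPRS total score only, and run only if at least one dose is significant on the primary endpoint. Efficacy data from more than 45 days after the last dose are excluded (SAP 10.1). Nothing says how a missing responder status is treated.

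The PGI-C responder GEE in SAP 10.3.2 has the same form: "treatment-by-visit interaction using an exchangeable working correlation structure in the model".

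**The concern.** There are two distinct issues.

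- **Covariate.** Two models of one variable in the same section use different baseline adjustment, and no reason is given. If baseline CGI-S is prognostic, leaving it out of the GEE costs power.
- **Missing data.** The MMRM uses the likelihood of all observed scores and is valid if missingness depends on observed data (MAR). An unweighted GEE on observed visits generally is not. Protocol 6.1.8 provides for discontinuation because of disease progression, so dropout related to earlier CGI-C scores is plausible, although no rate is given.

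At stake is the most readable summary of a key secondary variable. If the responder odds ratio and the MMRM contrast point different ways, differing missing-data assumptions would be one possible cause that the plan gives no means of ruling out. The GEE may also supply the pooled-dose contrast that SAP 10.3.1 adds when both doses succeed on the primary endpoint.

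**Working it through.** **1. The plan's own figure.** The 25% enters only the PSPRS power statement (SAP 4.3: 110 per arm, effect sizes 0.56 and 0.28, two-sided 5% split by Bonferroni to 2.5% per dose).
- Subjects with data: 110 × 0.75 = 82.5 per arm.
- High dose: 0.56 × √(82.5/2) = 3.597; 3.597 − 2.241 = 1.356; power 0.912.
- Low dose: 0.28 × √(82.5/2) = 1.798; 1.798 − 2.241 = −0.443; power 0.329.

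The stated figure of about 90% is reproduced for the high dose. No rate, power or precision is given for CGI-C responders, so everything below rests on assumptions.

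**2. Simulation set-up (assumed).** Two arms, no site effect, the eight CGI-C visits, and a latent progression score standing in for CGI-C, with response when it is at or below a cut-off. Week 52 response is about 20% on placebo and 20 to 35% on active. The fitted model is a logit GEE with exchangeable working correlation. Standard errors are rescaled to 110 per arm by √(n/110).

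**3. Adding baseline CGI-S, no missing data.** Relative efficiency = (z adjusted / z unadjusted)².

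| Correlation with Week 52 latent score | Log-OR (SE) unadjusted | Log-OR (SE) adjusted | SE ratio | Relative efficiency |
|---|---|---|---|---|
| about 0 | 0.603 (0.307) | 0.604 (0.307) | 1.000 | 1.00 |
| 0.17 | 0.624 (0.308) | 0.624 (0.308) | 1.001 | 1.00 |
| 0.35 | 0.637 (0.309) | 0.655 (0.312) | 1.010 | 1.04 |
| 0.53 | 0.610 (0.308) | 0.673 (0.319) | 1.036 | 1.13 |

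Last row: 0.673/0.610 = 1.103; 1.103/1.036 = 1.065; 1.065² = 1.13. The gain arises because the conditional log odds ratio moves away from zero by more than its SE grows. The SE itself does not fall.

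**4. Bias of the planned GEE at Week 52.** Dropout between visits is logistic in the previous visit's score with slope k, calibrated to about 25% missing by Week 52. Bias = log-OR from observed visits minus log-OR from the same data without dropout.

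| Dropout mechanism | OR, full data | OR, planned GEE | Bias | Bias/SE | Bias with CGI-S added |
|---|---|---|---|---|---|
| Effect; completely at random | 2.15 | 2.15 | 0.000 | 0.00 | 0.003 |
| Effect; same in both arms, k = 1.5 | 2.15 | 2.23 | +0.038 | 0.10 | +0.036 |
| Effect; same, k = 3 | 2.15 | 2.28 | +0.059 | 0.15 | +0.056 |
| Effect; score-driven on placebo only, k = 3 | 2.15 | 2.29 | +0.064 | 0.17 | +0.060 |
| Effect; opposite directions, k = 1.5 | 2.15 | 1.93 | −0.108 | −0.29 | −0.115 |
| Effect; opposite directions, k = 3 | 2.15 | 1.82 | −0.164 | −0.43 | −0.170 |
| No effect; same, k = 1.5 | 0.95 | 0.94 | −0.012 | −0.03 | −0.012 |
| No effect; score-driven on placebo only, k = 3 | 1.03 | 1.09 | +0.056 | 0.14 | +0.053 |
| No effect; opposite directions, k = 3 | 1.03 | 0.84 | −0.208 | −0.53 | −0.216 |

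Under no effect with one shared mechanism the arms are exchangeable, so zero bias is expected by symmetry. A different assumed progression model with a true OR of 1.80 gave +0.033 for a shared mechanism and −0.005 for mechanisms differing between arms, each with a simulation error of about 0.04. The smaller biases are therefore close to simulation noise; those of −0.11 to −0.21 are not.

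**5. Reading the table.** The last column barely differs from the bias column, so the covariate does not repair the missing-data problem. The sign is not fixed across scenarios. The largest values need the worse subjects to leave on placebo and the better ones on active.

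**The case against.** The strongest case against acting is that nothing confirmatory uses this model. It lies outside the error-controlled family. The CGI-C hypotheses H13 and H23 rest on the MMRM, which has the covariate and is valid under MAR, and Protocol 8.1.3.2 describes only that MMRM. With one dropout mechanism in all arms the bias is at most about 0.15 of a standard error. Larger values need arm-specific mechanisms for which the documents give no evidence. Adding a covariate to a logit model also changes the estimand to a conditional odds ratio.

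All of this stands as a limit on importance. The change of estimand is minor, because the planned odds ratio is already conditional on site.

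Several stronger readings are tempting but not supported:

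- A reader might infer that adjustment narrows the confidence interval. With a logit link it does not (SE ratio 1.00 to 1.04).
- A reader might infer that the GEE is valid only if data are missing completely at random. Missingness that depends only on terms in the model (treatment, site, visit) is also acceptable.
- A reader might infer that any disagreement with the MMRM must come from missing data. A dichotomised score on a logit scale can differ from a mean-score contrast even with complete data.
- A reader might take 25% as the CGI-C dropout rate, or dropout after worsening as established. The first is a PSPRS planning assumption; for the second, Protocol 6.1.8 only says how such discontinuations are recorded.
- A reader might want CGI-S in the PGI-C GEE too. The PGI-C MMRM has no baseline term (SAP 10.3.2, Protocol 8.1.3.2), so there is no inconsistency to remove.

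**Conclusion.** The point holds as a minor, cheap improvement. The CGI-C responder GEE omits a prognostic candidate that its companion MMRM uses, and it rests on a stricter missing-data assumption than that MMRM.

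Under the assumed scenarios, the log odds ratio bias at Week 52 is about 0 (no effect) to 0.03–0.06 (true effect) with a common dropout mechanism. It is up to about 0.2, roughly half a standard error at 110 per arm, when mechanisms differ between arms. No direction can be claimed in advance. The power given up is 0 to 13% in test efficiency, depending on a correlation the documents do not report.

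These figures depend on the assumed response rates, progression model, correlations and 25% missing, and show only a plausible range. The confirmatory CGI-C result is not in question.

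**What to change.** Make two separate changes in SAP 10.3.1.

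1. Add baseline CGI-S to the CGI-C responder GEE and state that the odds ratio is conditional on it. Present this as a gain in power, not as a narrower interval.
2. Make the GEE valid under MAR. Either impute the CGI-C score by multiple imputation, dichotomise, fit the GEE to each completed data set and combine by Rubin's rules, or use an inverse-probability-weighted GEE with weights modelled on treatment, baseline CGI-S and earlier CGI-C scores. Either route depends on a reasonable imputation or weight model, which should be specified in advance. Use the same missing-data handling for the PGI-C GEE in SAP 10.3.2, without adding CGI-S there.

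The cost is a few lines of SAP text, modest programming (the SAP already plans multiple imputation for PSPRS) and a slightly different odds ratio. No new data, visits or alpha are needed.
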